OFFICIAL TITLE: Oral Health Educational Methods in Adolescence

NCT number: **03216746**

Date:17/07/2018

Study Protocol and Statistical Analysis Plan

Study population and sample size

The investigation followed the parameters of the Declaration of Helsinki and was approved by the Human Ethics Committee of the Federal University of Paraná (case number 51712315.4.0000.0102). The description of this clinical trial followed the recommendations made by CONSORT and the extension to cluster randomized trials¹⁹. The study was registered in the clinicaltrials.gov database under number NCT03216746.

Clinical trial randomized by clustering involving four arms in a 1: 1: 1: 1 ratio to the four intervention groups. The randomized allocation was performed using the classes as sample units. The courses were ordered alphabetically by name and allocation was generated by the software *Stata* version 12.0. A total of 28 classes were selected and randomly allocated to an interventional group by a blinded investigator, which did not participate in the study. The analysis was done in the individual unit. Adolescents of both sexes, aged 14 to 19 years, enrolled in a technical high school in the city of Curitiba, Paraná, Brazil were evaluated. Written informed consent was obtained prior to randomization from the participant or from the legal guardian when the age of the participant was less than 18 years.

Exclusion criteria were: adolescents with some physical or mental condition that made interventions impossible and those using fixed orthodontic devices at the time of clinical examination. Cluster unit areas of technical education related to the

health area, including dental technician, were excluded. The duration of the study was from July to December 2016.

The comparison between two independent groups was used for the sample calculation considering the unequal variances. For this calculation, the outcome was considered the "knowledge score" (KS). In a pilot study, it was found that the standard deviation of the KS from the "oral guidance" group was 2.56, while in the "video" group it was 1.96. In the same study, the difference detected between the groups was 0.53 points in the knowledge score. Therefore, considering a 5% significance level and 80% statistical power, a sample value of 108 individuals was found for each group, totaling 216 participants. Estimating a loss of 35% for each group, the final sample totaled 317 individuals.

Pilot study

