A pilot study was carried out with the objective of testing the suitability and methodological applicability of the instruments used. In addition, this step allowed us to verify the application dynamics of the instruments and the average time spent with each participant. Fifteen adolescents aged 14 to 19 years, with the same socioeconomic characteristics as the study population, were selected who did not participate in the main study. The methodological design was adequate; however, some terms of the questionnaire were modified to allow greater understanding on the part of the adolescents.

Interventions

Interventions were performed at the individual level within each cluster. The study included four phases (Figure 1), and the educational interventions or their different associations were evaluated through the knowledge score (KS) and oral

clinical indexes. In Phase I/baseline, the participants answered a questionnaire (pre-test) and were evaluated clinically. In phase II, the 28 classes were randomly allocated into two groups: 14 classes received oral guidance (OG) and 14 classes received video guidance (VG). Both methods (oral guidance and guidance by video) had the same thematic content. In the next phase (III), the groups were again divided into four groups (7 groups in each group), and for two of them, a smartphone App was developed so that reinforcement messages were sent during a period of 30 days. Shortly after this period (phase IV), the participants answered the questionnaire again (follow-up test) and were reassessed clinically.

Oral guidance with standardized content was performed by one of the researchers (GM) previously trained, and included aspects on general, oral health and, especially, on periodontal diseases. This guidance was carried out in the classroom, in a group, with approximately 20 adolescents, providing an environment of discussions on the subjects addressed. The duration was approximately 15 minutes. The elaboration of the video had the participation of three actors, two acting as adolescents and the third as a dental surgeon. The video had a total duration of 14 minutes and was applied in the classroom itself, in a group, with approximately 20 adolescents, without, however, allowing a later discussion of the subject.

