Those responsible for adolescents also answered a questionnaire containing socioeconomic and demographic information according to criteria of the Brazilian Association of Research Companies²⁰.

Oral clinical examination

Clinical examination was performed by a single examiner calibrated ($K \geq 0.83$) and blinded as to the intervention used and which verified the presence of dental biofilm through the simplified oral hygiene index (OHI-S)²¹ and gingival bleeding (GBI)²². The tests were performed in two stages: Phase I and 20 weeks after in Phase V (Figure 1). The subjects were examined in a classroom where they were seated in chairs, and the evaluations were done individually, using gauze, artificial light and a millimeter probe.

Statistical analysis

Statistical analysis was performed on an individual level. Chi-square test was used to analyze the categorical variables. The numerical variables were submitted to the *Kolmogorov-Smirnov* test to verify the normality of the data, obtaining values of $P < 0.05$. Thus, non-parametric tests were used to verify the association between the means of KS, OHI-S and GBI among the different intervention groups. The OHI-S variable was dichotomized in: $OHI-S > 1$ (high dental biofilm index) and $OHI-S \leq 1$ (low dental biofilm index). *Kruskal Wallis* and *Mann-Whitney* tests were used for independent samples and *Wilcoxon's* test for paired samples. The level of significance adopted for all analyzes was 5%. The analyzes were performed using SPSS software version 20.0 (SPSS Inc., Chicago, IL, USA).

[figure not shown]

Figure 1. Flow chart demonstrating the different phases of the study.

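### Classes were allocated but pupils are analysed as independent, so the between-arm tests exceed 5% if classes differ

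*Combined protocol and SAP*

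**What the plan says.** **Allocation.** Under Study population and sample size: "The randomized allocation was performed using the classes as sample units". Under Interventions, in phase II "14 classes received oral guidance (OG) and 14 classes received video guidance (VG"), and in phase III "the groups were again divided into four groups (7 groups in each group"). That makes 28 classes in four arms of 7, all of them given oral or video guidance, with the App added in two arms. Guidance was delivered in the classroom to groups of about 20, with discussion in the oral version. The plan also says that its description follows the CONSORT extension for cluster trials.

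**Analysis.** Under Statistical analysis: "Statistical analysis was performed on an individual level". The stated aim is that "non-parametric tests were used to verify the association between the means of KS, OHI-S and GBI among the different intervention groups". Kruskal-Wallis and Mann-Whitney are named for independent samples and Wilcoxon as the "test for paired samples. The level of significance adopted for all analyzes was 5" per cent. The section does not mention class, clustering or an ICC. It does not say whether the between-arm tests use follow-up scores or changes, or whether the Wilcoxon test is run arm by arm or pooled.

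**Timing.** Interventions describes a four-phase study and says: "Shortly after this period (phase IV), the participants answered the questionnaire again (follow-up test) and were reassessed clinically". Oral clinical examination says: "The tests were performed in two stages: Phase I and 20 weeks after in Phase V (Figure 1").

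**The concern.** All the named tests assume independent observations. Pupils in one class share a teaching session, classmates and, in the oral arm, a discussion, so their scores or changes may be correlated. Arms differ by whole classes, and any class-to-class variation then enters the comparison between arms. A test that counts pupils treats that variation as if it had averaged out over every individual. The nominal 5% is then too low, and a difference between arms may be declared that is only a difference between the classes allocated to them. This bears on the primary outcome, the knowledge score (KS), and on the two clinical indexes, OHI-S and GBI. The chi-square test has the same limitation if it is used to compare dichotomised OHI-S between arms.

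A second, lesser concern is how a paired before-after result would be read. With 0 of 28 classes left without education, a change from Phase I mixes education with time, answering the same five statements again, and re-examination.

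**Working it through.** **Inputs from the documents.** Four arms of 7 classes; level 5%, taken as two-sided. Pupils per class are not stated directly. The planned totals give 216/28 = 7.7 (taken as 8) and 317/28 = 11.3 (taken as 11). The only group size stated is about 20, for teaching. Since 28 × 20 = 560 exceeds 317, 20 is used as an upper case.

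**Assumed.** ICC of 0.01, 0.05 or 0.10 for whichever quantity is tested (follow-up score or change).

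**Formulas.** Design effect DE = 1 + (m − 1) × ICC, with m pupils per class. Approximate true level:
- Kruskal-Wallis, four arms: P(χ² on 3 df > 7.815/DE).
- Mann-Whitney, or paired Wilcoxon on changes: 2 × [1 − Φ(1.96/√DE)].

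Example with m = 11 and ICC = 0.05: DE = 1 + 10 × 0.05 = 1.5. Kruskal-Wallis: 7.815/1.5 = 5.21, giving 15.7%. Mann-Whitney: 1.96/√1.5 = 1.60, giving 11.0%.

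**Simulation check.** 28 classes, no arm difference and no mean change. Each value is a class effect N(0, ICC) plus an individual term N(0, 1 − ICC); 3,000 replicates.

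| m | ICC | DE | Kruskal-Wallis, pupils: formula | Same: simulated | Mann-Whitney or Wilcoxon, pupils: formula | Kruskal-Wallis, 28 class means: simulated |
|---|---|---|---|---|---|---|
| 8 | 0 | 1.00 | 5.0% | 5.2% | 5.0% | 4.4% |
| 8 | 0.01 | 1.07 | 6.3% | 6.7% | 5.8% | 4.5% |
| 8 | 0.05 | 1.35 | 12.2% | 11.2% | 9.2% | 4.2% |
| 8 | 0.10 | 1.70 | 20.4% | 19.6% | 13.3% | 4.5% |
| 11 | 0 | 1.00 | 5.0% | 4.6% | 5.0% | 3.8% |
| 11 | 0.01 | 1.10 | 6.9% | 6.4% | 6.2% | 4.2% |
| 11 | 0.05 | 1.50 | 15.7% | 15.9% | 11.0% | 4.0% |
| 11 | 0.10 | 2.00 | 27.2% | 26.6% | 16.6% | 5.1% |
| 20 | 0 | 1.00 | 5.0% | 5.3% | 5.0% | 5.2% |
| 20 | 0.01 | 1.19 | 8.7% | 8.1% | 7.2% | 4.1% |
| 20 | 0.05 | 1.95 | 26.1% | 25.4% | 16.0% | 4.3% |
| 20 | 0.10 | 2.90 | 44.1% | 43.2% | 25.0% | 3.9% |

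The plan's 5% is therefore reproduced when pupils are independent (ICC = 0), and it is lost as the ICC rises. Simulated Mann-Whitney tests of 14 against 14 classes agree with the formula column: 8.5% to 15.3% at ICC 0.05 to 0.10 with 8 to 11 pupils, and 15.9% to 23.8% with 20.

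**A KS-like score.** With integer scores of 0 to 5 (assumed latent mean 3, SD 1.2, correlation about 0.5; 2,000 replicates; 8/11 pupils per class), Kruskal-Wallis on individual changes rejects 9.7%/13.7% at ICC 0.05 and 17.4%/22.6% at 0.10. On class means it rejects 3.6% to 5.1%.

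**Which ICC matters.** On follow-up scores, ordinary lasting differences between classes are enough to inflate the between-arm tests; simulated rates were 12% to 42% at ICC 0.05 to 0.10 with 8 to 20 pupils. On changes, a class effect that is the same at both visits cancels, and inflation needs classes to differ in their average change.

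**Paired Wilcoxon.** With only a stable class effect, simulated rates were 3.6% to 5.6%, so the level holds. If classes differ in their change, one arm of 7 classes gave 8.6%/10.2% at ICC 0.05 and 12.4%/16.4% at 0.10 (8/11 pupils).

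**The case against.** The strongest reply is that the size is assumed. The documents give no ICC, and at 0.01 the excess is small enough to ignore. That stands, and it is why a range is given. It does not remove the point: the plan allocates and teaches by class, gives no ground for an ICC of zero, and has a valid analysis available from the same data.

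A reader might infer that the paired Wilcoxon test fails under any class clustering. It does not, because pairing removes a class effect that is stable over time. Only class differences in change inflate it.

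A reader might also infer that the plan means to prove education effective from before-after tests, or that the lack of an uneducated arm is a design fault. The text supports neither. It names a test for paired samples without giving it a role, and its stated aim is comparison among intervention groups. Comparing oral guidance, video and App reinforcement with one another is a legitimate design, and drift common to all arms does not bias that comparison. What remains is a caution about reporting.

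Finally, a reader might take the 20 weeks as contradicting a follow-up soon after the 30-day App period. It need not, since the interval between Phase I and the start of the App is not stated. Only the phase numbers conflict, and no result depends on them.

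**Conclusion.** The point holds for the between-arm tests. Individual-level Kruskal-Wallis and Mann-Whitney tests do not hold 5% if classes differ in the quantity analysed. Under assumed ICCs of 0.05 to 0.10, Kruskal-Wallis rejects about 11% to 27% of the time with 8 to 11 pupils per class and about 25% to 43% with 20. At 0.01 the figure is about 6% to 9%. The same test on the 28 class means stays at or below about 5%, within simulation error. These figures rest on assumed ICCs, equal class sizes and normally distributed values; the 0-to-5 score gives somewhat lower rates and the same conclusion.

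The paired Wilcoxon problem is conditional and secondary. The phase-number conflict is clerical: Figure 1 was not available in the text reviewed and may resolve it.

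**What to change.** 1. **Between-arm conclusions.** State in Statistical analysis that they rest on a class-level analysis. One option keeps the named tests and applies Kruskal-Wallis and Mann-Whitney to the 28 class means, of either follow-up score or change from Phase I, with the choice stated. A 7-against-7 comparison can still reach significance: the smallest two-sided exact P value is 2/3,432 = 0.0006. The other option is a mixed model with a class random effect, the baseline score and small-sample degrees of freedom. For dichotomised OHI-S, compare class proportions or use the corresponding clustered model. Report the ICC.
2. **Paired results.** Label them descriptive, say whether they are per arm or pooled, and state that with all 28 classes educated they are not evidence that education works.
3. **Phases.** Reconcile Interventions, Oral clinical examination and Figure 1 under one numbering.

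Cost: revised text and a re-analysis. The study ran in 2016 and class is the allocation unit, so no new data or visits are needed. Nominal power falls. With 28 × 11 = 308 pupils, the information is that of about 308/1.5 = 205 independent pupils at ICC 0.05, or 308/2 = 154 at 0.10. Much of that loss is precision that the individual-level analysis only appeared to have.
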